## APPENDIX X: EXCEPTIONS FROM ISO 14155 COMPLIANCE

Minimal exceptions to ISO 14155:2020 compliance are expected, though these exceptions do not affect the safety and protection of the clinical investigation subjects and do not compromise data quality and security.

- This clinical investigation provides market approved devices, which will be used within their intended purpose, thus clinical investigation labelling will not be applied, a separate investigator Brochure will not be created, and clinical device accountability will not be set up.
- The study will not be submitted for review to the Competent Authority, only standard vigilance reporting will be observed. Local and/or regional requirements might be still applicable and will be tracked in a study specific Safety Plan.
- Financial disclosures will not be collected from the Investigators.

1.0 SYNOPSIS OF STUDY DESIGN

1.1 Purpose of the Statistical Analysis Plan

This statistical analysis plan (SAP) is intended to p	provide a detailed and comprehensive description of
the planned methodology and analysis to be used	for the JETi Registry clinical
investigation. This plan is based on the	Clinical Investigation Plan.

1.2 Clinical Investigation Objectives

The objective of the JETi Registry is to collect real-world data on the safety, performance, and clinical benefits of the JETi System for the treatment of thrombosis in the peripheral vasculature.

1.3 Clinical Investigation Design

The JETi Registry is a prospective, single-arm, multicenter study to collect real-world data on the safety, performance, and clinical benefits of the JETi System for the treatment of acute and subacute thrombosis in the peripheral vasculature. This is a post-market study and will register approximately 280 subjects at approximately 30 centers globally. Subjects participating in this registry will be followed through their 12-month follow up visit.

After JETi procedure,

subjects will be evaluated at discharge, 30 days, and 12 months.

1.4 Endpoints

1.4.1 Primary Endpoints

1.4.1.1 Arterial Subjects

For subjects treated for arterial or arteriovenous thrombosis, the primary endpoints are:

Clot removal grade for each JETi-treated target vessel(s) from pre-JETi angiogram to post-JETi
angiogram (post-JETi thrombectomy and prior to any adjunctive therapies to treat underlying
culprit lesions) per the grades in Table 1 (vessel basis). The independent imaging core laboratory
will be responsible for assessing this endpoint.

Table 1. Clot Removal Grade

Grade I	< 50% reduction
Grade II	50 - <95% reduction
Grade III	95 – 100% reduction

Composite of JETi-related major adverse events (MAEs), defined as the following JETi-related
events: device-related death, major amputation of the treated limb (arterial subjects only), or
major bleeding up to 30 days post-JETi procedure and as adjudicated by a clinical events
committee (CEC) (subject basis).

Statistical Analysis Plan

1.4.1.2 Venous Subjects

For subjects treated for lower extremity DVT, the primary endpoints are

Percent of treated vessel(s) with ≥ 75% venous thrombus reduction from pre-JETi venogram
to final venogram (post-JETi AND after any/all adjunctive therapies to treat underlying culprit
lesions) via modified Marder score. The independent imaging core laboratory will be responsible
for assessing this endpoint.

If no adjunctive therapies or devices are used after JETi, post-JETi modified Marder score is also final score.

 Composite of JETi-related major adverse events (MAEs), up to 30 days post-JETi procedure, defined as the following JETi-related events, adjudicated by a clinical event committee (CEC): (1) death, (2) symptomatic pulmonary embolism (PE), (3) major bleeding, (4) re-thrombosis of JETitreated vessel(s).

1.4.2 Descriptive Endpoint(s)

[figure not shown]
1.4.2.1 All Subjects

- Procedure-related death as adjudicated by a CEC.
- JETi-related AEs collected at discharge, 30 days, and 12 months follow-up, and as adjudicated by a CEC.
- Procedure-related access site complications such as hematoma, pseudoaneurysm (false aneurysm), perforation, as adjudicated by a CEC.

Statistical Analysis Plan

• Treatment Used: The number and percentage of patients having each of the following treatments:

Quality of life (QoL) questionnaire: SF-12 at baseline, 30-day and 12-month follow-up.

1.4.2.2 Arterial Subjects

- Clot removal grade for each JETi-treated target vessel from pre-JETi angiogram to final
 angiogram (post-JETi thrombectomy and after any/all adjunctive therapies and prior to removal of
 the vascular sheath) per the grades in Table 1.
- Components of the MAE including device-related death, major amputation of treated limb (arterial subjects only), and major bleeding up to 30 days post-JETi as adjudicated by a CEC.
- Ankle Brachial Index* (ABI) of treated limb(s) at baseline and 30 days.
- Rutherford* classification at baseline and 30 days.
 * only applicable to subjects with lower limb arterial thrombus.
- Rate of re-thrombosis of JETi-treated vessel at 30 days, and 12 months, as assessed by investigator/physician reported.
- Patency as determined by duplex ultrasound at baseline, 30-day, and 12-month follow-up. Note that this endpoint will only apply to subjects treated for arteriovenous thrombus.
- Vessel patency: assessed by the independent imaging core laboratory using the Modified Thrombolysis in Myocardial Infarction (TIMI) classification called TIPI (Thrombo-aspiration in Peripheral Ischemia)¹ (Table 3) for each JETi-treated vessel, assessed using angiogram.
 - At post-JETi timepoint (post-JETi thrombectomy and prior to any adjunctive therapies to treat underlying culprit lesions)
 - At final timepoint (post-JETi thrombectomy and after any/all adjunctive therapies and prior to removal of the vascular sheath)

¹ de Donato G, Pasqui E, Sponza M, et al. Safety and Efficacy of Vacuum Assisted Thrombo-Aspiration in Patients with Acute Lower Limb Ischaemia: The INDIAN Trial. *Eur J Vasc Endovasc Surg*. 2021;61(5):820-828. doi:10.1016/j.ejvs.2021.01.004

Statistical Analysis Plan

If no adjunctive therapies or devices are used after JETi, post-JETi TIPI score is also final TIPI score.

Table 3. Thrombo-aspiration in Peripheral Ischemia (TIPI)

Description	TIPI score
No recanalization of the thrombotic occlusion	0
Incomplete or partial recanalization of the thrombotic occlusion with no distal flow	1
Incomplete or partial recanalization of the thrombotic occlusion with any distal flow	2
Complete recanalization of the thrombotic occlusion with normal distal flow	3

- Acute success, as per TIPI score (Table 3), per core lab assessment:
 - Device success: Near complete or complete recanalization of occluded vessel, defined as post-JETi TIPI 2-3.
 - Technical success: Near complete or complete recanalization of occluded vessel, defined as final TIPI 2-3, using JETi system and any other adjunctive device or procedures.
 - Procedural success: Technical success with no JETi-related MAEs within 5 days of registration or by discharge, whichever occurs first.

1.4.2.3 Venous Subjects

- Percent of treated vessels with ≥75% clot reduction from pre-JETi venogram to post-JETi venogram (post-JETi thrombectomy and before any adjunctive therapies to treat underlying culprit lesions) via modified Marder score. The independent imaging core laboratory will be responsible for assessing this endpoint.
- For subjects not treated for lower extremity DVT (i,e. upper extremity DVT (UE DVT)), Clot removal grade for each JETi-treated target vessel from pre-JETi venogram to final venogram (post-JETi thrombectomy and after any/all adjunctive therapies and prior to removal of the vascular sheath) per the grades in **Table 1**.
- Components of the JETi-related MAE including up to 30 days post-JETi adjudicated by a CEC death, symptomatic pulmonary embolism (PE), major bleeding and rethrombosis of target vessel(s).
- Re-thrombosis in the JETi-treated vessel(s) at 30-day and 12-month follow up, as assessed by investigator/physician reported, and as adjudicated by CEC.
- The Villalta Post Thrombotic Syndrome (PTS) severity scale at baseline, 30-day, and 12-month follow-up. Note that this assessment will apply only to subjects with lower extremity DVT.

Statistical Analysis Plan

- Edema component score from the Villalta Post Thrombotic Syndrome (PTS) severity scale at baseline, 30-day, and 12-month follow-up.
- A 7-point Likert Scale for leg pain at baseline, discharge, 30-day, and 12-month follow-up.
- Venous patency and compressibility as determined by duplex ultrasound at baseline, 30-day, and 12-month follow-up.
- Acute success,
 assessed by core laboratory:
 - Device success: Post-JETi thrombus removal grade II-III
 - occurs after JETi system and any other adjunctive device or procedures.
 - Procedural success: Technical success with no JETi-related MAEs within 5 days of registration or by discharge, whichever occurs first.

If no adjunctive therapies or devices are used after JETi, post-JETi is also final score

2.0 ANALYSIS CONSIDERATIONS

2.1 Analysis Populations

All registered subjects will be included in the analyses. The point of registration in the Registry is when a JETi Catheter is introduced into the intended vasculature of an enrolled subject during the procedure (Day 0). A subject who is enrolled but not registered in this study will be considered as a screen failure.

[figure not shown]
Consenting up to 5 days post-JETi procedure is acceptable. In these cases, the point of registration will be the same and any procedural information will be entered post-consent, and adverse events (AEs) will be collected retrospectively from the point of registration (Day 0).

2.2 Statistical Methods

2.2.1 Descriptive Statistics for Continuous Variables

For continuous variables (e.g., age, BMI, etc.), results will be summarized with the numbers of observations, means, and standard deviations, with quartiles, minimums, maximums, and 95% confidence intervals, where specified.

2.2.2 Descriptive Statistics for Categorical Variables

Statistical Analysis Plan

2.3 Endpoint Analysis

2.3.1 Primary Endpoint(s)

2.3.1.1 Arterial Subjects

For subjects treated for arterial thrombosis

all endpoints are

descriptive. There will be no hypothesis testing, and there are no statistical power considerations.

Primary Effectiveness Endpoint:

Clot removal grade for each JETi-treated target vessel from pre-JETi angiogram to post-JETi angiogram (post-JETi thrombectomy and prior to any adjunctive therapies to treat underlying culprit lesions) per the grades. Summary statistics (number and % of treated vessel) of clot removal grade from pre- to post-JETi thrombectomy will be summarized.

Primary Safety Endpoint:

Composite of JETi-related major adverse events (MAEs), defined as the following JETi-related events: device-related death, major amputation of the treated limb (arterial subjects only), or major bleeding up to 30 days post-JETi procedure and as adjudicated by a clinical events committee (CEC). It will be summarized as the number of events and the percentage of subjects with events.

2.3.1.2 Venous Subjects

Primary Effectiveness Endpoint:

• For subjects treated for lower extremity DVT, the primary effectiveness endpoint is the percent of treated vessel(s) with ≥ 75% venous thrombus reduction from pre-JETi venogram to final venogram (post-JETi AND after any/all adjunctive therapies to treat underlying culprit lesions) via modified Marder score. If no adjunctive therapies or devices are used after JETi, post-JETi modified Marder score is also final score. This endpoint is a binary outcome defined as whether there is 75% reduction in modified Marder score from baseline at the limb level.

Statistical Analysis Plan

Primary Safety Endpoint:

The primary safety endpoint is the composite of JETi-related MAEs, up to 30 days post- JETi procedure (death, symptomatic pulmonary embolism (PE), major bleeding, or re-thrombosis of JETi-treated vessel(s)) for subjects treated for lower extremity DVT and as adjudicated by a clinical events committee (CEC).

It will be summarized as the number of events and the percentage of subjects with events.

2.3.2 Descriptive Endpoint(s) Analyses

All descriptive endpoints will be summarized descriptively.

Statistical Analysis Plan

A total of approximately 280 subjects will be registered in this Registry.

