2.9 Handling of Missing Data

Every effort will be made to acquire all necessary data. Analysis will be based on available data with missing data excluded. Any unused or spurious data will be noted as appropriate in the final report. However, impact of missing data may be assessed in the sensitivity analysis.

Statistical Analysis Plan

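### Twelve-month re-thrombosis: the visible SAP gives no rule for subjects who die or are lost before 12 months, so the reported rate depends on who is dropped

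*SAP*

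**What the plan says.** Re-thrombosis at 12 months is listed for both groups. SAP 1.4.2.2 (arterial) has "Rate of re-thrombosis of JETi-treated vessel at 30 days, and 12 months, as assessed by investigator/physician reported". SAP 1.4.2.3 (venous) has "Re-thrombosis in the JETi-treated vessel(s) at 30-day and 12-month follow up", reported by the physician and also adjudicated by the events committee.

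The visible analysis text is short. SAP 2.3.2 says "All descriptive endpoints will be summarized descriptively". SAP 2.9 says "Analysis will be based on available data with missing data excluded" and adds "However, impact of missing data may be assessed in the sensitivity analysis", so the sensitivity analysis is optional. SAP 2.1 says "All registered subjects will be included in the analyses". SAP 3.3 tabulates deaths, withdrawals and losses by visit but does not link them to the re-thrombosis rate. Neither the visible contents list nor the acronym list of the SAP names a survival or competing-risk method.

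The Protocol foresees incomplete follow-up. Under 7.3.1, surveillance stops at death or withdrawal. Under 5.6, only vital status is kept after withdrawal.

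**The concern.** Re-thrombosis accrues over a year in which some subjects will die and others will leave. A percentage then needs a stated denominator, and the visible rules point to more than one. SAP 2.1 brings in every registered subject, while SAP 2.9 removes those with missing data. Protocol 6.0 also treats unexpected re-thrombosis as an adverse event, and SAP 3.2 summarises adverse events as a percentage of subjects for all registered subjects. The same event could therefore appear in the final report as two different percentages.

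The two simple counts err in opposite directions. Treating lost subjects as event-free lowers the rate, because events after loss go unseen. Keeping only subjects with known 12-month status raises it, because event-free deaths and losses leave the denominator while events already observed stay in.

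The stake is highest for arterial subjects without arteriovenous thrombosis. ABI and Rutherford class stop at 30 days, and duplex is for arteriovenous cases only (Protocol Table 5), so re-thrombosis is their only listed 12-month vessel outcome. If the denominator is left open, it may be chosen after the data are seen.

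**Working it through.** **Inputs.** The documents give no re-thrombosis, death or loss rate and no re-thrombosis figure to reproduce. All rates below are assumed. Hazards are constant, loss is independent of the event, and every visit falls on day 365, so the visit window plays no part.

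**Formulas.** For net 12-month risks r (re-thrombosis), d (death) and l (loss), let a = −ln(1−r), b = −ln(1−d), c = −ln(1−l).

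- Target, the cumulative incidence with death competing: a/(a+b) × [1 − exp(−(a+b))].
- A, observed events over all registered: a/(a+b+c) × [1 − exp(−(a+b+c))].
- B, observed events over events plus event-free attenders: A / [A + exp(−(a+b+c))].

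**Worked case, 15% / 10% / 20%.** a = 0.1625, b = 0.1054, c = 0.2231.

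- Target = 0.1625/0.2679 × (1 − 0.765) = 14.3%.
- A = 0.1625/0.4910 × (1 − 0.612) = 12.8%.
- B = 0.1284/(0.1284 + 0.612) = 17.3%.

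**Range** (differences in points, from unrounded values):

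| r / d / l (assumed) | Target | A | B |
|---|---|---|---|
| 10 / 2 / 10% | 9.9% | 9.4% (−0.5) | 10.6% (+0.7) |
| 15 / 10 / 15% | 14.3% | 13.2% (−1.1) | 16.9% (+2.6) |
| 15 / 10 / 20% | 14.3% | 12.8% (−1.4) | 17.3% (+3.1) |
| 20 / 10 / 15% | 19.0% | 17.6% (−1.4) | 22.4% (+3.3) |
| 20 / 10 / 20% | 19.0% | 17.2% (−1.9) | 22.9% (+3.9) |
| 20 / 20 / 20% | 18.0% | 16.3% (−1.7) | 24.1% (+6.1) |

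With no death and no loss, all versions agree.

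**Milder counts.** At 20/10/15%, counting 12-month attenders only gives 20.0% (+1.0). Dropping losses but keeping event-free deaths in the denominator gives 20.2% (+1.2).

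**Informative loss.** In a simulation of 1,000,000 subjects at 20/10/15%, death and loss were made 3 or 4 times as likely after re-thrombosis. The attenders-only figure fell to 16.1% (−2.9) or 14.5% (−4.5).

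**Scale.** SAP 2.3.2 states "A total of approximately 280 subjects will be registered in this Registry". The standard error of a 15% rate is √(0.15 × 0.85/280) = 2.1 points. With an assumed half split (n = 140) it is 3.0 points.

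**The case against.** The strongest reply is that the criticised method is not written down. The body of SAP 2.2.2 (categorical variables) is not visible, there is a gap after the sentence in 2.3.2, the visible contents jump from 2.3.2 to 2.6 and from 2.6 to 2.9, and Protocol 8.8 has a redaction in its missing-data text. This stands: the point is conditional on the withheld text. It does not show that leaving out missing data suits this endpoint, and nothing visible elsewhere repairs it.

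A reader might infer four stronger things that the documents do not support:

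- That the SAP prescribes a crude percentage with no allowance for death or loss. A crude percentage is an inference, and SAP 2.9 does mention an optional sensitivity analysis.
- That the rate could be several points off in either direction. With independent loss, the downward error is about 1 to 2 points in the 15–20% settings above. More than that needs heavier loss, a higher event rate, or death and loss that are clearly likelier after re-thrombosis.
- That these are the registry's only 12-month durability results. Twelve-month duplex patency is listed for arteriovenous and venous subjects.
- That arterial and venous rates would be made non-comparable by higher arterial mortality. No mortality figure is given, SAP 2.6 analyses the groups separately, and ascertainment already differs between them.

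Further points narrow the remedy. Silent re-thrombosis found at a scheduled scan is interval-censored, and a cumulative incidence dated at detection does not cure that. Censoring at last contact is itself biased if loss is informative. The arterial rate is worded per vessel, so a per-subject estimate changes the unit. The Protocol's retention measures (phone or virtual visits, repeated calls, a letter) may keep loss below the upper values assumed here.

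**Conclusion.** The concern holds in a limited form. On the visible text, 12-month re-thrombosis has no stated denominator and no rule for death or loss, and missing data are excluded, so the published rate will shift with who is dropped. At low event and attrition rates the shift is under 1 point. At 15–20% re-thrombosis with 10% death and 15–20% loss, it is about 3 to 4 points upward if event-free deaths and losses are excluded, and about 1 to 2 points downward if lost subjects count as event-free. The upward shift is similar in size to, or somewhat larger than, the sampling error.

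These figures rest on assumed rates, constant hazards and independent loss, and the conclusion falls if withheld text already sets an estimator. Severity is minor, since no visible test or success criterion uses the endpoint.

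**What to change.** Amend SAP 2.3.2, with a matching exception in 2.9, unless the withheld text already covers this:

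- Estimate time to first reported re-thrombosis per subject by cumulative incidence (Aalen-Johansen), with death as a competing event and censoring at last contact. Define that as the last contact at which re-thrombosis was ascertained, because Protocol 5.6 accepts indirect contact for vital status.
- Report 30-day and 12-month estimates with 95% confidence intervals and numbers at risk, separately for arterial, arteriovenous and lower-extremity DVT subjects.
- Keep crude counts alongside, with their denominators and with the vessel-level count for arterial subjects.
- Make the missing-data sensitivity analysis mandatory for this endpoint, since censoring assumes that loss is non-informative.
- State that events found only at a scheduled scan are dated at detection.

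The cost is SAP wording, one standard SAS procedure and slightly more analysis work. It also needs dates of re-thrombosis, death and last contact. The 5-day and 30-day event cut-offs imply that event dates are captured, but the case report forms are provided separately, so this should be confirmed.

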2.6 Timing of Analysis

Analysis for the primary endpoints will be performed after all registered subjects (within arterial or DVT groups) have reached their 30-day follow-up visit. Analysis for final report will be conducted after all registered subjects have completed the 12-month follow-up visit.

Analysis will be performed separately for arterial and venous subjects.

[figure not shown]
2.9 Handling of Missing Data

Every effort will be made to acquire all necessary data. Analysis will be based on available data with missing data excluded. Any unused or spurious data will be noted as appropriate in the final report. However, impact of missing data may be assessed in the sensitivity analysis.

Statistical Analysis Plan

2.10 Poolability Issue

3.0 DESCRIPTIVE ENDPOINTS AND ADDITIONAL DATA

3.1 Baseline and Demographic Characteristics

The following baseline and demographic variables will be summarized for all registered subjects: gender, age, ethnicity, race, medical history, etc.

3.2 Adverse Events

All device-, and procedure-related adverse events and all serious adverse events will be summarized for all registered subjects in this trial in terms of the number of events, the percentage of subjects with events.

Statistical Analysis Plan

3.3 **Subject Early Termination**

Subject early termination reasons including deaths, withdrawals, lost-to-follow-up, etc. will be summarized at all scheduled visits.

3.4 **Protocol Deviation**

Protocol deviations will be summarized for subjects in whom a protocol deviation was reported.

4.0 **DOCUMENTATION AND OHER CONSIDERATIONS**

All analyses will be performed using SAS® for Windows, version 9.4 or higher.

Statistical Analysis Plan

5.0 **ACRONYMS AND ABBREVIATIONS**

Acronym or Abbreviation	Complete Phrase or Definition
ABI	Ankle Brachial Index
ALI	Acute Limb Ischemia
AV	Arteriovenous
CDT	Catheter Directed Thrombolysis
CEC	Clinical Events Committee
CIP	Clinical Investigation Plan
DVT	Deep Vein Thrombosis
IVC	Inferior Vena Cava
MAE	Major Adverse Event
OUS	Outside of US
PE	Pulmonary Embolism
PG	Performance Goal
PTS	Post Thrombotic Syndrome
QOL	Quality of Life
SAE	Serious Adverse Event
SAP	Statically Analysis Plan
SF-12	Short-Form Health Survey-12
TIMI	Thrombolysis in Myocardial Infarction
TIPI	Thrombo-aspiration in Peripheral Ischemia

Statistical Analysis Plan

6.0 **REFERENCES**

2. SAS Institute Inc. 2015. SAS/STAT® 14.1 User's Guide. Cary, NC: SAS Institute Inc.

7.0 **APPENDICES**

Statistical Analysis Plan

APPENDIX A: STATISTICAL ANALYSIS PLAN REVISIONS
